9. ADVERSE EVENTS

9.1. OVERVIEW

The Principal Investigator is responsible for the detection and documentation of events meeting the criteria and definition of an AE (adverse event) or SAE (serious adverse event) as described in this protocol. All AEs and SAEs will be recorded in the source documents and on the appropriate electronic CRF(s). All data will be reviewed periodically by the SKCCC Safety Monitoring Committee (SMC), which may provide recommendations about withdrawing any participant and/or terminating the study because of safety concerns.

Adverse events that are classified as serious according to the definition of health authorities must be reported promptly and appropriately to the Principal Investigators in the trial, IRBs and health authorities. This section defines the types of AEs and outlines the procedures for appropriately collecting, grading, recording and reporting them. Information in this section complies with *21CFR 312; ICH Guideline E2A: Clinical Safety Data Management: Definitions and Standards for Expedited Reporting; and ICH Guideline E-6: Guidelines for Good Clinical Practice*; and applies the standards set forth in the National Cancer Institute (NCI), *Common Terminology Criteria for Adverse Events, Version 4.0 (May 28, 2009)*.

9.2. DEFINITIONS

9.2.1 Adverse Events

An AE is any occurrence or worsening of an undesirable or unintended sign, symptom, laboratory finding, or disease that occurs during participation in the trial. An AE for participants will be followed until it resolves or until 30 days after the participant terminates from the study, whichever comes first. All AEs will be reported as specified in sections 9.2.2 and 9.2.3. **Error! Reference source not found.** Whether they are or are not related to disease progression or study participation.

9.2.2 Adverse Reaction and Suspected Adverse Reaction

An adverse reaction means any adverse event caused by a drug. Adverse reactions are a subset of all suspected adverse reactions for which there is reason to conclude that the drug caused the event.

Suspected adverse reaction (SAR) means any adverse event for which there is a reasonable possibility that the drug caused the adverse event. For the purposes of safety reporting, 'reasonable possibility' means there is evidence to suggest a causal relationship between the drug and the adverse event. A suspected adverse reaction implies a lesser degree of certainty about causality than adverse reaction, which means any adverse event caused by a drug (21 CFR 312.32(a)).

9.2.3 Serious Adverse Event or Serious Suspected Adverse Reaction

An AE or SAR is considered "serious" if, in the view of the Investigator, it results in any of the following outcomes:

- Death: A death that occurs during the study or that comes to the attention of the Principal Investigator during the protocol-defined follow-up period as defined in section 4.0 must be reported whether it is considered treatment-related or not.
- A life-threatening event: An AE or SAR is considered "life-threatening" if, in the view of the Investigator, its occurrence places the subject at immediate risk of death. It does not include an AE or SAR that, had it occurred in a more severe form, might have caused death.
- An event that requires intervention to prevent permanent impairment or damage. An important medical event that may not result in death, be life threatening, or require hospitalization may be considered serious when, based upon appropriate medical judgment, it may jeopardize the participant and may require medical or surgical intervention to prevent one of the outcomes listed above.

9.2.4 Unexpected Adverse Events

A SAR is considered "unexpected" if it is not identified in the package insert and/or drug label, or protocol, or is not listed at the specificity, or severity that has been observed (21 CFR 312.32(a)).

9.3. COLLECTING AND RECORDING ADVERSE EVENTS

9.3.1 Methods of Collection

Adverse events for recipients will be collected from the time the participant receives the first dose of study medication as specified in section 9.4. Adverse events will be followed until the time an event is resolved or until 30 days after the recipient completes or terminates from the study, whichever comes first. The methods for collecting AEs will include:

- Observing the participant.
- Questioning the participant in an objective manner.
- Receiving an unsolicited complaint from the participant.

An abnormal value or result from a clinical or laboratory evaluation (e.g., a radiograph, an ultrasound, or an electrocardiogram) can also indicate an AE if it is determined by the Investigator to be clinically significant. If this is the case, it must be recorded in the source document and as an AE on the appropriate AE form(s). The evaluation that produced the value or result should be repeated until that value or result returns to normal or can be explained and the participant's safety is not at risk.

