6. STUDY STATISTICS

This is a phase I study of Idelalisib, an orally-administered, selective inhibitor of Phosphoinositide 3 kinase (PI3K)- δ . It has been successfully used pre-transplant to induce partial and complete responses in many B-cell derived malignancies. In this study Idelalisib will be evaluated in the post-transplant setting. Patients receiving a standard of care allogeneic hematopoietic stem cell transplant from any source: cord, marrow, or peripheral blood will be eligible. Patients will be randomized in a 2:1 ratio to either 100 mg Idelalisib twice daily from day 90 (\pm 10 days) following transplant, Arm A, or a placebo, Arm B, and monitored for toxicity until day 270.

Study treatment plan: Idelalisib day +90 [+/- 10 days), 100mg twice daily, and at least 5 days after the discontinuation of filgrastim if ANC is greater than 1,000 and PLT 50>Gi/L and <grade 2 aGVHD. Patient's Idelalisib will be dose adjusted for the expected toxicities of Idelalisib including pneumonitis, hepatitis, neutropenia, thrombocytopenia and loose stools.

Primary endpoint and design: The primary goal of this study is to evaluate the safety of Idelalisib as post-transplantation maintenance in patients undergoing an allogeneic BMT. In addition to the allowed dose reductions, a safety monitoring plan will be implemented to ensure that other treatment-limiting events are not elevated. The study will be monitored between the date of randomization and day 270 post-transplant. For safety monitoring, treatment-limiting toxicities will be defined as Idelalisib interruption for >14 days, or other grade 3 or higher adverse events as defined by CTCAE IV not captured in the protocol for dose de-escalation. The trial will assume that, *a priori*, the probability of these events in both arms of the study will follow a Beta (0.10, 0.90) prior distribution. This distribution corresponds to an assumption that 10% of patients might experience a treatment-limiting toxicity.

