5: 0.10, 0.30	59.0%	10.1, 20.2
6: 0.10, 0.35	70.7%	9.3, 18.5
7: 0.10, 0.40	83.4%	8.1, 16.1
8: 0.10, 0.45	90.0%	7.3, 14.5
9: 0.10, 0.50	94.4%	6.6, 13.1

Secondary endpoint:

1. Event-free survival at one year.

Analysis Plans:

Toxicities will be summarized descriptively by grade and type. Cumulative incidences of aGVHD, relapse, and NRM will also be computed using Fine and Gray's method for competing risks. Treatment of relapse/progression, graft failure, and death are considered competing risks for GVHD; relapse/progression is a competing risk for NRM; and death before relapse/progression is a competing risk for relapse/progression. In addition, we plan to report aGVHD incidences with only graft failure and death regarded as competing risks.

Using the Kaplan-Meier method, the probability of 1-year event-free survival will be estimated and reported with 95% confidence intervals. The proportions of patients who are event-free at 1 year will also be estimated with a 95% exact binomial confidence interval.

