9.3.2 Severity of Adverse Events to be collected

All AE grades will be defined per NCI-CTCAE version 4.0 criteria unless otherwise specified starting at the beginning of Idelalisib treatment

With the following exceptions, all AEs of grade 3 or higher will be collected from the time at which the participant receives the first dose of study medication as specified in section 9.4 until the time the participant completes or prematurely withdraws from the study:

- Haematological abnormalities will be collected as AEs per NCI-CTCAE v. 4.0 criteria once participants have achieved platelet and neutrophil recovery.
- All episodes of allograft failure and of acute, grade III or IV GVHD will be collected as AEs.

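### Sections 9.2.1 and 9.3.1 conflict on when a laboratory abnormality is an AE, so a grade 3 or higher chemistry value can be left out of the safety results by judgement

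*Combined protocol and SAP*

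**What the plan says.** Section 9.2.1 gives the general definition: "An AE is any occurrence or worsening of an undesirable or unintended sign, symptom, laboratory finding, or disease" arising during participation. It does not ask whether the finding is clinically important.

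Section 9.3.1 deals with abnormal results from clinical or laboratory evaluations. Such a result "can also indicate an AE if it is determined by the Investigator to be clinically significant"; when that judgement is made, the result must go into the source document and onto the AE form.

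Section 9.3.2 sets the collection threshold: "all AEs of grade 3 or higher will be collected from the time" of first dose, subject to listed exceptions. One of these reads: "Haematological abnormalities will be collected as AEs per NCI-CTCAE v. 4.0 criteria once participants have achieved platelet and neutrophil recovery". Chemistry has no equivalent line.

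Section 6 defines the TLT as an interruption of more than 14 days or "other grade 3 or higher adverse events as defined by CTCAE IV not captured in the protocol for dose de-escalation". The planned safety analysis is: "Toxicities will be summarized descriptively by grade and type". Section 6 describes no analysis of the measured laboratory values.

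**The concern.** Safety against placebo is the trial's primary objective, and the comprehensive metabolic panel (CMP) is measured in both arms on one calendar. If investigators may decide that an abnormal value is not important enough to record, the same value can be an AE for one patient and nothing for another, with both decisions compliant.

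After transplant many abnormal values have a competing explanation, so there is room for such decisions. The filter also acts before attribution. Section 9.4 already provides a five-level causality code, and the placebo arm is there to account for background abnormalities. A value set aside earlier never reaches either of them.

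**Working it through.** No figure in the plan bears on this point, so the check is a comparison of texts and a count of scheduled measurements.

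**1. Is an abnormal chemistry value an AE?** Under 9.2.1, yes, if it is undesirable or unintended. Under 9.3.1, it is to be recorded if judged clinically significant. The two agree when the investigator says yes and part when the investigator says no.

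**2. Does grading settle it?** No. Sections 9.3.2 and 9.4.1 apply CTCAE v4.0 to events already called AEs. The Master AE log in Section 4 (grade 2 and higher) and the grade 3 threshold in 9.3.2 likewise apply to AEs, not to laboratory values. Only haematology has a line that starts from CTCAE criteria.

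**3. Which analytes have another route?** The calendars list nine CMP analytes: BUN, creatinine, sodium, potassium, chloride, AST, ALT, total bilirubin and alkaline phosphatase. Section 5.2 gives numeric thresholds for three of them (AST, ALT, bilirubin). The other 9 − 3 = 6 have none.

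**4. Trace two values.**

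- *A potassium value in the CTCAE grade 3 range, judged not clinically significant.* Under 9.2.1 it is an AE, is collected under 9.3.2, appears in the by-grade summary and counts in the grade 3+ limb of the TLT, since no dose rule covers it. Under 9.3.1 it is not recorded and appears in neither.
- *An ALT value above 5x ULN.* Section 5.2 holds study drug if no other cause explains the value, and stops it permanently above 20x ULN whatever the cause. A resulting hold of more than 14 days is a TLT without any AE being declared. This route is incomplete: the 5x rule contains a causal judgement, and a hold of 14 days or less does not count. Sections 4 and 6 list hepatitis among the dose-adjusted toxicities, so a hepatic event would normally fall outside the grade 3+ limb anyway. For hepatic chemistry the 9.3.1 condition therefore acts mainly on the AE summary.

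**5. Is there a fallback analysis?** Section 6 has none. Both calendars schedule CBC and CMP after first dose at Cycle 1 Day 15 (1), Cycles 2–6 Day 1 (5), 30 days after last dose (1) and Month 12 (1): 1 + 5 + 1 + 1 = 8 visits. With the Section 6 sample size and full attendance that is 8 × 30 = 240 panels in Arm A and 8 × 15 = 120 in Arm B, 360 in all. For a patient treated to day +270, the last two visits fall after the TLT window.

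**6. Can the loss be sized?** Not from the documents. They give neither the share of grade 3+ chemistry values likely to be judged unimportant nor the share of TLTs that would arise only through chemistry outside the dose rules.

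**The case against.** The strongest reply is that 9.3.1 opens a route and does not close one. It says that a result can also indicate an AE, never that only a significant result can, and its examples are imaging and ECG. Section 9.4.1 describes grade 3 as severe and undesirable, so such a value already meets 9.2.1 and would be hard to call unimportant. The haematology line in 9.3.2 can be read as delaying collection until counts recover, with no implication that chemistry is treated more loosely.

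This reading is fair, and it is why the point is a conflict between sections and not a settled rule that drops chemistry. It does not remove the conflict: 9.3.1 names laboratory evaluations, attaches recording to the judgement, and is the section that tells staff how to collect AEs.

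Four stronger readings are tempting but unsupported:

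- *All chemistry toxicity reaches the results by opinion.* The numeric AST, ALT and bilirubin rules in Section 5.2 contradict this.
- *The 14% serious hepatotoxicity rate in Section 5.1 can be discounted and set against the 0.10 delta.* The first is a one-arm rate for one toxicity; the second is a between-arm difference in TLT.
- *The loss of stopping-rule sensitivity can be calculated.* It would need an assumed share of all TLTs lost, for which the documents offer no basis.
- *The filter favours one arm.* Section 1 describes the trial as double blind, and nothing shows that laboratory patterns would reveal allocation.

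**Conclusion.** The point holds as an inconsistency in AE ascertainment that touches the primary safety endpoint. For creatinine, sodium, potassium and alkaline phosphatase, a grade 3 or higher value can be missing from both the AE summary and the grade 3+ limb of the TLT. For AST, ALT and bilirubin the exposure is mainly in the AE summary.

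The expected effect is under-recording and inconsistent recording in both arms. Its size is unknown, and no numerical claim should be attached to it. The conclusion rests on two readings: that staff would follow 9.3.1 when deciding what to record, and that the toxicities summarised in Section 6 are the recorded AEs. Section 6 does not state the second outright, but it names no other source. The point is worth correcting because the correction is cheap; it does not undermine the design.

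**What to change.** 1. Reconcile 9.2.1 and 9.3.1, and extend 9.3.2, so that scheduled chemistry results of CTCAE v4.0 grade 3 or higher are collected as AEs, in line with the haematology rule.
2. Add to Section 6 a by-arm table of worst post-dose CTCAE grade and shift from Cycle 1 Day 1, derived from the scheduled CBC and CMP values independently of AE reporting. State the time window.
3. Leave the TLT definition as it is. Replacing its AE limb with machine-derived grades would redefine the primary endpoint, since an isolated transient value could then count as treatment-limiting. The Section 6 operating characteristics assume control-arm TLT rates of 5% or 10%.

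The cost is a sentence or two in Section 9, one in Section 6, and a short grading program. No tests or visits are added, and the dose-adjustment rules are untouched. The downside is that reported laboratory toxicity rates will be somewhat higher in both arms. Because the TLT counts recorded AEs, TLT counts may rise a little too, so the team should confirm that the assumed control rates still look reasonable.

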9.3.2 Severity of Adverse Events to be collected

All AE grades will be defined per NCI-CTCAE version 4.0 criteria unless otherwise specified starting at the beginning of Idelalisib treatment

With the following exceptions, all AEs of grade 3 or higher will be collected from the time at which the participant receives the first dose of study medication as specified in section 9.4 until the time the participant completes or prematurely withdraws from the study:

- Haematological abnormalities will be collected as AEs per NCI-CTCAE v. 4.0 criteria once participants have achieved platelet and neutrophil recovery.
- All episodes of allograft failure and of acute, grade III or IV GVHD will be collected as AEs.

9.4. GRADING AND ATTRIBUTION OF ADVERSE EVENTS

9.4.1 Grading Criteria

The study site will grade the severity of AEs experienced by study participants according to the criteria set forth in the National Cancer Institute's ***Common Terminology Criteria for Adverse Events Version 4.0*** (published May 28, 2009). This document (referred to herein as the "NCI-CTCAE v. 4.0 manual") provides a common language to describe levels of severity, to analyze and interpret data, and to articulate the clinical significance of all AEs.

Severity of adverse events will be graded on a scale from 1 to 5 according to the following standards in the NCI-CTCAE v. 4.0 manual:

- Grade 1 = mild adverse event.
- Grade 2 = moderate adverse event.
- Grade 3 = severe and undesirable adverse event.
- Grade 4 = life-threatening or disabling adverse event.
- Grade 5 = death.

For additional information and a printable version of the NCI-CTCAE v. 4.0 manual, go to <http://ctep.cancer.gov/reporting/ctc.html>

ATTRIBUTION DEFINITIONS

Adverse events will be categorized for their relation to one or more of the following:

- bone marrow transplantation
- investigational study medication, Idelalisib
- other protocol-directed study procedures

The Principal Investigator will do the initial determination of the relation, or attribution, of an AE to study participation and will record the initial determination on the appropriate eCRF and/or SAE reporting form. The relation of an AE to study participation will be determined using definitions in Table 1.

TABLE 1: ATTRIBUTION OF ADVERSE EVENTS

Code	Descriptor	Relationship (to primary investigational product and/or other concurrent mandated study therapy)
Unrelated Categories		
1	Unrelated	The adverse event is clearly not related.
2	Unlikely	The adverse event is unlikely related.
Related Categories		
3	Possible	The adverse event has a reasonable possibility to be related; there is evidence to suggest a causal relationship.
4	Probable	The adverse event is likely related.
5	Definite	The adverse event is clearly related.

9.5. REPORTING SERIOUS ADVERSE EVENTS

Serious adverse events must be reported to the Johns Hopkins University IRB within 48 hours of occurrence

10. ETHICAL, REGULATORY, AND ADMINISTRATIVE CONSIDERATIONS

10.1. STATEMENT OF COMPLIANCE

This trial will be conducted in compliance with the protocol, current Good Clinical Practice (GCP) guidelines—adopting the principles of the Declaration of Helsinki—and all applicable regulatory requirements.

Prior to study initiation, the protocol and the informed consent documents will be reviewed and approved by the sponsor and an appropriate ethics review committee or institutional review board (IRB). Any amendments to the protocol or consent materials must also be approved by the Sponsor, the IRB and submitted to FDA before they are implemented.

10.2. INFORMED CONSENT

The principles of informed consent are described in the Code of Federal Regulations 21 CFR, part 50.

Participants or their legal guardians must be made aware of the investigational nature of this treatment protocol, and have the possible risks, hazards and benefits of the protocol explained to them. The information that is given shall be in a language understandable to the participant. No informed consent, whether oral or written, may include any exculpatory language through which the patient is made to waive or appear to waive any of their legal rights, or releases or appears to release the Principal Investigator, the institution, or its agents from liability for negligence.

The participant, or legal guardian, must be able to comprehend the informed consent and must sign the document prior to registration on study. This will occur between Day +60 after HSCT and Day +100. A copy of the informed consent will be given to a prospective participant for review. The attending physician, in the presence of a witness, will review the consent and answer questions. The participant will be informed that participation is voluntary and that he/she may withdraw from the study at any time, for any reason. The participant will receive a copy of the respective signed consent form.

10.3. PRIVACY AND CONFIDENTIALITY

A participant's privacy and confidentiality will be respected throughout the study. Each participant will be assigned a sequential identification number. This number, rather than the participant's name, will be used to collect, store, and report participant information.

10.4. INSTITUTIONAL REVIEW

The principles of Institutional Review Board (IRB) are described in the Code of Federal Regulations 21 CFR, part 56.

The Principal Investigator will obtain approval for the study from the IRB. The Principal Investigator must notify the IRB within 5 days of protocol deviations in emergency situations regarding patient safety. The Principal Investigator will be responsible for obtaining annual IRB renewal through the duration of the study, or more frequently if required by the IRB. Copies of the Principal Investigator's report and copies of the IRB's continuance of approval must be maintained in the regulatory binder located at the clinical site.

10.5. MONITORING PLAN

This is a DSMP Level II study under the SKCCC Data Safety Monitoring Plan (12/6/2012). Data Monitoring of this protocol will occur on a regular basis with the frequency dependent on the rate of subject accrual and the progress of the study. The protocol will be monitored internally at SKCCC by the Principal Investigator and externally by the SKCCC CRO in accordance with SKCCC guidelines. Trial monitoring and reporting will be done through the Safety Monitoring Committee (SMC) at SKCCC.

12. APPENDIX 1-4

Appendix 1: **Staging and grading of acute graft-versus-host disease**

1. Staging: Record the highest level of organ abnormalities during the assessment period:
Use the “rule of 9s” to compute percentage of body surface area for the skin assessment.
 - a. Skin
 - Stage I: Maculopapular rash < 25% of body surface
 - Stage II: Maculopapular rash 25-50% of body surface
 - Stage III: Generalized erythroderma (>50% of body surface)
 - Stage IV: Generalized erythroderma with bullous formations and desquamation
 - b. Intestinal Tract
 - Stage I > 500 ml/day
 - Stage II > 1000 ml/day
 - Stage III > 1500 ml/day
 - Stage IV > Severe abdominal pain, with or without ileus
 - c. Liver
 - Stage I: Bilirubin 2-3 mg/dL
 - Stage II: Bilirubin 3-6 mg/dL
 - Stage III: Bilirubin 6-15 mg/dL
 - Stage IV: Bilirubin > 15 mg/dL
2. Overall Clinical Grading of Severity of Acute GVHD:
 - Grade I: Stage 1-2 skin rash; no gut involvement; no liver involvement; no decrease in clinical performance
 - Grade II: Stage 1-3 rash; stage 1 gut involvement, or stage 1 liver involvement (or both); mild decrease in clinical performance
 - Grade III-Stage 2-3 skin rash; 2-3 gut involvement or stage 2-4 liver involvement (or both); marked decrease in clinical performance
 - Grade IV-Similar to Grade III with stage 2-4 organ involvement and extreme decrease in clinical performance

